6.2 Efficacy

6.2.1 Primary efficacy variable and analyses

6.2.1.1 Primary efficacy variable

- Absolute change from baseline in 6MWD after 20 weeks of treatment, i.e., 6MWD at 20 weeks minus 6MWD at baseline.

6.2.1.2 Primary analysis of primary efficacy variable

The primary efficacy analysis aims at evaluating the dose-response relationship of the primary and secondary efficacy variables for all randomized patients, who have remained in the study and adhered to study treatment according to the study protocol until Week 20 (“completers and treatment adherers” analysis). Therefore, the primary analysis will be performed in the PPS, a subset of the FAS comprising “compliant and adherent” patients (as much as possible, defined via validity criteria). To avoid bias, the PPS will also include those “compliant and adherent” patients who are “censored” due to CV death or a hospitalization for HF preventing the assessment of the relevant efficacy endpoints 20 weeks after randomization, to take place as planned. For missing post-baseline value due to CV death or study drug/study discontinuation due to HF, a worst case approach will be applied. The worst observation value (WOV) would be imputed as follows:

- 1) First, the worst change from baseline value by each treatment group will be calculated. If any of them is positive, the value would be set to 0.
- 2) Secondly the median of the worst changes from baseline value among all treatment groups would be calculated. The change from baseline value for all the missing data will be imputed with a multiplier 1.0 of this median value.
- 3) The WOV (i.e. imputed post-baseline value at week 20) will be calculated accordingly as baseline value + imputed change from baseline. If this imputed WOV for 6MWD is less than 0 (in case of either CV death or a hospitalization for HF preventing the measurement), then the WOV will be replaced with 0 and the imputed change from baseline will be modified to (- baseline value) accordingly.

All other patients with invalid/missing baseline value or missing post-baseline value due to other reasons than the above will be excluded from the PPS.

It is expected, that these are the only patients for whom missing observations need to be considered in the primary analysis. A “worst case” approach will be used, where the missing change from baseline value will be imputed with a multiple of the worst change from baseline value, which is possible given the individual baseline value observed in the respective treatment group, or 0 if the worst change in that treatment group is positive.

Statistical Analysis Plan

It is planned to perform a test for a dose-response signal, under the assumption of a nearly monotone dose-response relationship in the dose range considered. The MCP-Mod method (1) combining multiple comparison procedures (MCP) principles with modeling techniques will be used for the primary statistical analysis of the primary efficacy variable. This method allows the flexibility of modeling for dose estimation, while preserving the robustness to model misspecification associated with MCP procedures. The MCP-Mod method will be used based on SAS programs provided (2) and the results may be validated within R (3) with the actual DoseFinding package (4).

Assumptions

Five active doses of neladenoson bialanate will be used in this study: 5 mg, 10 mg, 20 mg, 30 mg, and 40 mg, as well as a placebo arm corresponding to a 0 mg dose.

The measurements of the primary efficacy variable are assumed to be normally distributed with the same standard deviation σ and independent between patients, respectively.

The following assumptions were made for the absolute change from baseline in 6MWD over 20 weeks:

- the expected mean effect under the placebo dose is assumed as an absolute increase from baseline of up to $\Delta = 0$ m with a standard deviation of $\sigma = 80$ m
- while the maximum observable mean effect under neladenoson bialanate within the dose range considered is assumed as an absolute increase of $\Delta = 40$ m with a standard deviation of $\sigma = 80$ m.

This results in an expected maximum effect size of $(40 - 0) / 80 = 0.5$.

It is assumed that the primary efficacy variable, denoted as Y , is observed for the 6 parallel groups corresponding to doses levels: (placebo =) $d_1 < d_2 < \dots < d_k$, where $k = 6$.

For patient j within treatment group i the response can then be described by the following model:

$$Y_{ij} = f(d, \boldsymbol{\theta}) + \varepsilon_{ij}, \quad \varepsilon_{ij} \sim N(0, \sigma^2), \quad i = 1, \dots, k, \quad j = 1, \dots, n_i,$$

where $f(\cdot)$ is parameterized by a vector of parameters $\boldsymbol{\theta}$ and ε_{ij} is the error term.

A candidate set with $M=5$ different dose response shapes $f(\cdot)$ based on four models was chosen for the MCP-Mod method. Table 6—1 displays the response expressions for the shapes in the candidate sets.

[figure not shown]
Figure 6—1 shows the corresponding dose-response shapes. The model parameters were obtained through discussions with experts in the clinical team, taking prior beliefs and uncertainty into account.

Statistical Analysis Plan

Table 6—1: Dose-response shapes used in the candidate set

Model	Response as function of dose d
Linear	d
Sigmoidal E_{max} 1	$40.1 d^4 / (9^4 + d^4)$
Sigmoidal E_{max} 2	$45 d^3 / (20^3 + d^3)$
E_{max}	$41.25 d / (1.25 + d)$
Quadratic	$2.667 d - 0.044 d^2$

Figure 6—1: Dose-response shapes used in the candidate set

Based on the standardized versions of the models in the candidate set and the sample size allocation planned for this study, the optimum contrast coefficients for the 5 contrast tests on the dose-response shapes can be derived for the primary variable.

Analysis

Step 1: Detection of dose-response signal

For detecting an overall trend, or a dose-response signal, each of the $M=5$ dose-response shapes in the candidate set will be tested, using a single contrast test based on the updated version of contrast coefficients taking the actual sample sizes per treatment group into account.

For each model m , $m = 1, \dots, 5$, in the candidate set

the null hypothesis $H_{0m}: c_m \mu_m^0 = 0$

will be tested against

Statistical Analysis Plan

Protocol No.: < BAY 1067197/17582 >

Page: 20 of 38

the respective 1-sided alternative hypothesis $H_{1m}: c_m \mu_m^0 > 0$,

where $\mu_m^0 = (\mu_{m1}^0, \dots, \mu_{m6}^0)' = (f_m^0(d_1, \boldsymbol{\theta}_m^0), \dots, f_m^0(d_6, \boldsymbol{\theta}_m^0))'$ and

f^0 is the standardized version of the dose-response model $f(d, \boldsymbol{\theta}) = \theta_0 + \theta_1 f^0(d, \boldsymbol{\theta}^0)$. In this parameterization, θ_0 is a location parameter and θ_1 is a scale parameter such that only $\boldsymbol{\theta}^0$ determines the shape of the model function.

The contrast coefficients $c_{m1} \dots c_{m6}$ for the m -th model are chosen such that they maximize the power to detect the underlying model. These optimal contrast coefficients depend only on the parameters in the standardized model function $\boldsymbol{\theta}^0$, which determine the model shape (1) and the actual group sample sizes (which is known after unblinding of the study). The i th member of the optimal contrast vector $\mathbf{c}_{opt,m}$ for testing the shape model m is proportional to

$$n_i(\mu_{mi}^0, \dots, \bar{\mu}), i = 1, \dots, 6,$$

where $\bar{\mu} = N^{-1} \sum_{i=1}^6 \mu_{mi}^0 n_i$. In case of unequal sample sizes per treatment arm, $\mathbf{c}_{opt,m}$ cannot be expressed in closed form and numerical optimization techniques are required (1, 3). The $\mathbf{c}_{opt,m}$ is derived by fulfilling the condition $\sum_{i=1}^6 c_{mi}^2 = 1$.

The single contrast test for detecting the m -th model shape is defined by

$$T_m = \frac{\sum_{i=1}^6 c_{mi} \bar{Y}_i}{S \sqrt{\sum_{i=1}^6 c_{mi}^2 / n_i}}, m = 1, \dots, 5, \quad \text{where } S^2 = \frac{\sum_{i=1}^6 \sum_{j=1}^{n_i} (Y_{ij} - \bar{Y}_i)^2}{N-6}.$$

Under the null hypothesis of no dose-response effect, i.e. $\mu_{d_1} = \dots = \mu_{d_6}$, the test statistic $T = (T_1, \dots, T_5)'$ follows a central multivariate t distribution with $N-6$ degrees of freedom and correlation matrix $R = (\vartheta_{ij})$, where $\vartheta_{ij} = \frac{\sum_{l=1}^6 c_{il} c_{jl} / n_l}{\sqrt{\sum_{l=1}^6 c_{il}^2 / n_l \sum_{l=1}^6 c_{jl}^2 / n_l}}$.

The final test statistic T_{max} is based on the maximum contrast test and a “proof-of-concept” dose-response relationship is detected if this maximum statistic T_{max} , and thus at least one single contrast test, is statistically significant, while controlling the familywise error rate at level α . If $q_{1-\alpha}$ denotes the multiplicity adjusted critical value, a dose-response signal is established if $T_{max} \geq q_{1-\alpha}$.

This analysis will be performed for the FAS and PPS populations, where the PPS analysis is the primary analysis.

If no candidate model is statistically significant, the procedure stops, indicating that a dose-response relationship cannot be established from the observed data.

Out of the statistically significant models in the candidate set a best model can be selected for the next step: modeling and estimation.

Step 2: Modeling and estimation of target doses

If a dose-response signal is established, the selected dose-response model(s) will be fitted to the observed data to estimate the model parameters.

The estimated dose-response model will be plotted against the doses including 90% confidence bands. Once the dose-response model has been successfully fitted to the data,

Statistical Analysis Plan

target dose(s) of interest are estimated. Given a clinically relevant effect Δ , a minimum effective dose (MED_{Δ}) associated with model $f(d, \theta)$ is defined as

$$MED_{\Delta} = \operatorname{argmin}_{d \in (d_1, d_6]} \{f(d, \theta) \geq f(d_1, \theta) + \Delta\}.$$

Estimates of MED_{Δ} will be calculated for a clinically relevant change in 6MWD assumed as $\Delta = 40$ m and potentially a plausible range of Δ values which will be defined based on the observed data. In addition, estimates considering confidence bounds for the predicted value at a certain dose may be used. The final choice of the target dose depends on the evaluation of the primary efficacy variable and other efficacy variables, as well as safety considerations.

Additionally change from baseline in 6MWD will be descriptively summarized by treatment and overall, and visit in PPS.

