7.3 Treatment assignment

The intention is to randomize approximately 288 patients to the doses 5 mg, 10 mg, 20 mg, 30 mg, 40 mg of neladenoson bialanate, and placebo according to an allocation ratio of 1:2:2:2:2:3, respectively.

At the baseline visit, the investigator will first perform all required pre-treatment examinations and will then randomize the qualified patients to one of the six treatment arms.

The randomization will be stratified by atrial fibrillation (AF): yes vs. no.

Enrollment into the AF stratum may be stopped (after the discussion between the sponsor and the Steering Committee) when the AF stratum constitutes 30% of the total expected enrollment.

The randomization lists will be provided by Bayer's Global Randomization Management Group. Randomization will be done using an interactive voice / web response system (IxRS).

A handbook describing how to use the IxRS will be provided to each study site.

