9.4 Efficacy

9.4.1 6MWD test

The 6MWD test is designed to evaluate a patient's exercise capacity while performing an everyday activity. During this study, a 6MWD test including Borg CR 10 Scale will be conducted at different time points as specified in Table 9—1, for further details on assessment refer to Section 16.3. A familiarization 6MWD test will be performed during the run-in phase. To avoid any interactions, it is not permitted to perform the familiarization test on the same day as the baseline (Week 0) 6MWD test. It is only allowed to randomize patients, if the walking distance determined at baseline is \geq 100 m and \leq 550 m.

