Sigmoidal Emax 1	$40.1 d^4 / (9^4 + d^4)$
Sigmoidal E _{max} 2	$45 d^3 / (20^3 + d^3)$
E _{max}	41.25 d / (1.25 + d)
Quadratic	$2.667 d - 0.044 d^2$

14 FEB 2017 Version: 1.0 Page: 61 of 85

[figure not shown]

Figure 10—1: Dose-response shapes used in the candidate set

Based on the standardized versions of the models in the candidate set and the sample size allocation planned for this study, the optimum contrast coefficients for the 5 contrast tests on the dose-response shapes can be derived.

Analysis

Step 1: Detection of dose-response signal

For detecting an overall trend, or a dose-response signal, each of the M=5 dose-response shapes in the candidate set will be tested, using a single contrast test based on the updated version of contrast coefficients taking the actual sample sizes per treatment group into account.

For each model m, m = 1, ..., 5, in the candidate set

the null hypothesis

$$H_{0m}: c_m \mu_m^0 = 0$$

will be tested against

the respective 1-sided alternative hypothesis

$$H_{1m}$$
: $c_m \mu_m^0 > 0$,

where
$$\mu_m^0 = (\mu_{m1}^0, ..., \mu_{m6}^0)' = (f_m^0(d_1, \boldsymbol{\theta}_m^0), ..., f_m^0(d_6, \boldsymbol{\theta}_m^0))'$$
 and

 f^0 is the standardized version of the dose-response model $f(d, \mathbf{\theta}) = \theta_0 + \theta_1 f^0(d, \mathbf{\theta}^0)$. In this parameterization, θ_0 is a location parameter and θ_1 is a scale parameter such that only $\mathbf{\theta}^0$ determines the shape of the model function.

A "proof-of-concept" dose-response relationship is detected if at least one single contrast test, is statistically significant, while controlling the family-wise error rate at level α .

This analysis will be performed for the FAS and PPS populations, where the PPS analysis is the primary analysis.

14 FEB 2017 Version: 1.0 Page: 62 of 85

If no candidate model is statistically significant, the procedure stops, indicating that a dose-response relationship cannot be established from the observed data.

Out of the statistically significant models in the candidate set a best model can be selected for the next step: modeling and estimation.

Step 2: Modeling and estimation of target doses

If a dose-response signal is established, the selected dose-response model(s) will be fitted to the observed data to estimate the model parameters.

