6.2.1.5 Additional analysis of primary efficacy variables

Adjusted primary analysis (dose-response test) of primary efficacy variables specified in Section 6.2.1.2 will be performed in PPS. Baseline values of 6MWD, age (as a continuous variable) and gender will be used as covariates.

Statistical Analysis Plan

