6.4.2 Subgroup analysis of efficacy variables

Primary and secondary analyses of primary efficacy variable will be performed based on key subgroups. Additionally primary efficacy variable will be descriptively summarized based on exploratory subgroups.

Secondary efficacy variables will be descriptively summarized based on key subgroups.

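### The primary MCP-Mod test is valid but unadjusted; adding baseline 6MWD and the AF stratum would gain from almost nothing to about 7 points of minimum power, for about 0.2 point if they predict nothing

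*SAP*

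**What the plan says.** The endpoint in SAP 6.2.1.1 is "6MWD at 20 weeks minus 6MWD at baseline". Protocol 10.3.2.2 models it as a function of dose plus independent normal error, and says that "each of the M=5 dose-response shapes in the candidate set will be tested, using a single contrast test". SAP 6.2.1.2 gives the statistic after the words "The single contrast test for detecting the m -th model shape is defined by": a contrast of raw group means over the pooled within-group SD, referred to a multivariate t distribution on N-6 df. If no contrast is significant, the procedure stops before any dose modeling.

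Protocol 7.3 states: "The randomization will be stratified by atrial fibrillation (AF): yes vs. no". AF then appears only as a baseline characteristic (SAP 6.1.2) and an exploratory subgroup (Protocol 10.3.2.1, SAP 4.5.4). For the latter, SAP 6.4.2 plans summaries only: "Additionally primary efficacy variable will be descriptively summarized based on exploratory subgroups".

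SAP 6.2.1.5 does plan an adjusted dose-response test in the PPS: "Baseline values of 6MWD, age (as a continuous variable) and gender will be used as covariates". It is an additional analysis and does not include AF.

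**The concern.** A change score gives baseline a fixed coefficient of 1. Any remaining regression of change on baseline stays in the error term and widens the SD in the denominator of every contrast. Likewise, if AF is prognostic, stratification balances it between arms but its variance still sits in the pooled SD.

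Three things make this worth attention. First, the margin is thin: 80.84% for the linear shape, against a target of at least 80% under every shape. Second, Step 1 is a gate. A significant additional analysis under SAP 6.2.1.5 cannot reopen it, so a more precise test helps the main conclusion only if it is primary in advance. Third, the 5 mg arm has only 18 evaluable patients, so chance baseline imbalance can move its raw mean change noticeably.

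**Working it through.** **Inputs from the documents.** One-sided family-wise alpha 5%; maximum effect 40 m; SD of change 80 m; evaluable group sizes 54/18/36/36/36/36 for 0/5/10/20/30/40 mg (N = 216); the five shapes in Protocol Table 10-1.

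**Assumptions, because the documents are silent.** Baseline SD s of 90, 100, 112 or 130 m; Week-20 SD equal to k·s with k = 1.0, 1.1 or 1.2; an AF difference of 10 to 30 m.

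**Step 1: reproduce the plan.** With contrasts c_i proportional to n_i(μ_i − μ̄), the simulated critical value is 1.965. Power at N = 216:

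| Shape | Simulated | Protocol Table 10-2 |
|---|---|---|
| Linear | 80.9 | 80.84 |
| Sigmoidal Emax 1 | 91.8 | 91.81 |
| Sigmoidal Emax 2 | 87.8 | 87.80 |
| Emax | 88.7 | 88.72 |
| Quadratic | 86.8 | 86.61 |

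The quadratic is scaled to a 40 m maximum. As printed, it peaks at 2.667²/(4 × 0.044) = 40.4 m, which gives about 87.4%.

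**Step 2: variance of change explained by baseline.** Fixing the SD of change at 80 m (variance 6400) determines the correlation:

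- r = (s² + k²s² − 6400) / (2ks²)
- R² = (r·k·s² − s²)² / (6400·s²)

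Example, s = 90 and k = 1: r = (8100 + 8100 − 6400)/16200 = 0.605. Then r·s² − s² = −3200, and R² = 3200²/(6400 × 8100) = 0.20.

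**Step 3: adjusted power, linear shape.** There were 100,000 simulated trials per case, each fitted by least squares with arm, baseline and AF on N-8 df, so the cost of estimating two coefficients is included. Cells show R², then power.

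| Week-20 SD | s = 90 | s = 100 | s = 112 | s = 130 |
|---|---|---|---|---|
| equal to baseline | 0.20, 87.8% | 0.16, 86.4% | 0.13, 85.2% | 0.09, 84.1% |
| 10% larger | 0.11, 84.5% | 0.07, 83.2% | 0.04, 82.2% | 0.02, 81.3% |
| 20% larger | 0.04, 82.0% | 0.02, 81.2% | 0.002, 80.8% | 0.002, 80.8% |

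Against 80.9% unadjusted, the gains run from −0.1 to +6.9 points, with a median of 1.8 over the twelve cells. At R² = 0 adjusted power is 80.7%, a loss of about 0.2 point. A variant with 30% AF, stratified blocks and random loss from 288 to 216 patients gives −0.2 at R² = 0, +3.4 at 0.10 and +7.0 at 0.20.

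**Cross-check from the plan's own table.** Removing 10% of the variance is roughly like having 216/0.9 = 240 evaluable patients, for which Table 10-2 gives 84.48%. At the planned 75% evaluable rate that is 240/0.75 = 320 randomized, 32 more than 288.

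**Step 4: AF alone.** AF share was set to one third so that it balances exactly in every arm. A 30 m AF difference gives 81.1% unadjusted and 81.8% adjusted; at 10 to 20 m the change is 0.2 point or less. With 30 m, type I error is 4.6% unadjusted and 4.9% adjusted. With a baseline R² of 0.10 it is 5.0% both ways.

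**Step 5: chance imbalance at 5 mg.** Take s = 100 and k = 1. The slope of change on baseline is −3200/10000 = −0.32. The SE of the baseline difference from placebo is 100·√(1/18 + 1/54) = 27 m, so a one-SE imbalance shifts the raw difference in change by about 0.32 × 27 = 9 m, against a 40 m target.

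**The case against.** The design meets its stated target without adjustment, and four of the five shapes have 86.6% to 91.8% power. SAP 6.2.1.5 already prespecifies a baseline-adjusted test, and baseline carries nearly all of the gain. What remains is which test is primary, plus an AF term that adds little power and whose omission is conservative. All of this stands, and it is why the point is an improvement and not a correction.

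The 7-point figure needs both the smallest baseline SD tried and equal SDs at the two visits. A larger Week-20 SD is plausible. Only baseline is range-restricted: Protocol 9.4.1 says "It is only allowed to randomize patients, if the walking distance determined at baseline is" between 100 and 550 m. The worst-case rule in SAP 6.2.1.2 ("The change from baseline value for all the missing data will be imputed with a multiplier 1.0 of this median value") also adds Week-20 spread. In the rows with a larger Week-20 SD the best gain is 3.6 points. That stands too: 7 points is an assumed case, not a bound.

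The simulations contain no imputed patients, whose change is truncated at minus baseline. That limits the precision of the power figures; it does not alter the direction of the trade. Finally, the covariate list for multiple imputation in SAP 6.2.1.4.2 is open-ended, so AF could enter there, though it is not named.

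The objection does not remove the asymmetry: a loss of about 0.2 point at worst, against several points where baseline is moderately predictive.

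**Conclusion.** The concern holds as a recommended efficiency improvement. The primary test is valid and reaches 80%, but it omits a measured baseline and the only stratification factor. Adjusting would move minimum power from 80.9% to between 80.8% and 87.8% under the assumptions tried, or to about 80.7% if baseline and AF predict nothing. The gain rests on an R² that the documents do not let a reader fix: about 3 points at 0.10 and about 7 at 0.20. The case for AF is mainly that the analysis should reflect the stratified randomization. Confidence is medium, because the size depends on the unknown correlation between baseline and Week 20.

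**What to change.** Before unblinding, amend SAP 6.2.1.2 and align Protocol 10.3.2.2 so that the primary test uses a linear model with treatment group, baseline 6MWD and AF stratum as randomized. Apply the five MCP-Mod contrasts to the adjusted means with their covariance matrix, and take the critical value from the resulting correlation matrix on N-8 df. Use the same adjusted means and covariance in Step 2, so that detection and dose estimation rest on one model. Add AF to the model in SAP 6.2.1.5, and keep the present unadjusted test as a sensitivity analysis.

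The amendment should also say whether the adjustment carries into the analyses that inherit 6.2.1.2: the FAS multiple imputation (including the complete-data df in Appendix 9.4), the secondary endpoints, the key subgroups and the Japan-only repeat.

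The cost is wording and programming, part of which SAP 6.2.1.5 already requires, and two of 210 residual df. Baseline 6MWD and AF stratum are already collected.

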The estimated dose-response model will be plotted against the doses including 90% confidence bands. Once the dose-response model has been successfully fitted to the data, target dose(s) of interest are estimated. Given a clinically relevant effect Δ , a minimum effective dose (MED_{Δ}) associated with model $f(d, \theta)$ is defined as

$$MED_{\Delta} = \operatorname{argmin}_{d \in (d_1, d_6]} \{ f(d, \boldsymbol{\theta}) \geq f(d_1, \boldsymbol{\theta}) + \Delta \}.$$

Estimates of MED_{Δ} will be calculated for a clinically relevant change in 6MWD assumed as $\Delta = 40$ m and potentially a plausible range of Δ values which will be defined in the SAP. In addition, estimates considering confidence bounds for the predicted value at a certain dose may be used. The final choice of the target dose depends on the evaluation of the primary efficacy variable and other efficacy variables, as well as safety considerations.

Modeling and estimation will be performed for the FAS and PPS populations as well as for relevant subgroups.

Further details will be described in the SAP.

As a secondary analysis pairwise comparisons of the active neladenoson bialanate dose groups with the placebo group will be performed without controlling the family-wise error rate.

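### The SAP leaves any MED target other than 40 m to be set from the results, although the protocol says the SAP will define it, and 40 m is itself the assumed maximum effect

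*SAP*

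**What the plan says.** Both documents define the MED in Step 2 of the MCP-Mod analysis as the smallest dose above 0 and up to 40 mg at which the fitted effect over placebo is at least Delta.

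- **Fixed Delta.** The SAP (6.2.1.2, Step 2) says MED estimates "will be calculated for a clinically relevant change in 6MWD assumed as" 40 m. Protocol 10.3.2.2 gives the same value. No other value appears in either document.
- **Further Deltas.** Both documents make them optional, in the same phrase: "and potentially a plausible range of" Delta values. The protocol ends the sentence "values which will be defined in the SAP". The SAP ends it "values which will be defined based on the observed data".
- **Planning assumption.** Both assume a placebo change of 0 m and continue: "while the maximum observable mean effect under neladenoson bialanate within the dose range considered is assumed as an absolute increase of" 40 m, with SD 80 m.
- **Model used.** "Out of the statistically significant models in the candidate set a best model can be selected for the next step", after which "the selected dose-response model(s) will be fitted to the observed data to estimate the model parameters".
- **Other outputs.** The fitted curve is plotted with 90% confidence bands, and "estimates considering confidence bounds for the predicted value at a certain dose may be used". SAP 6.2.1.3 adds 90% intervals for each dose against placebo.

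SAP section 7 gives two approval dates and no description of changes.

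**The concern.** The protocol gives the SAP a pre-specification task, and the SAP passes it on to the trial results. The two sentences cannot both be followed. Step 2 comes after the contrast test and the model fit, so as worded the further Deltas may be chosen once the fitted curve is known. On a given curve, choosing Delta amounts to choosing the MED.

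This would matter little if the fixed Delta were comfortably within reach. It is not, because 40 m is the ceiling of the planning scenario. A trial that goes exactly as planned will often have a fitted curve that peaks just short of 40 m, and there will then be pressure to report an MED at some lower value. The study objective is to find the Phase III dose, so the target dose should not depend on a threshold picked afterwards.

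**Working it through.** **Inputs.** Protocol 10.4: 216 evaluable patients (54 on placebo, 18 on 5 mg, 36 on each of 10, 20, 30 and 40 mg), which is 75% of 288 randomized. Protocol 10.3.2.2: SD 80 m, maximum effect 40 m, one-sided 5% level (10.3.2), five candidate shapes (Table 10-1).

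**1. Reproduce the stated power.** Contrasts are proportional to n_i(mu_i - weighted mean), and the test uses the maximum of five correlated t statistics with 216 - 6 = 210 df. With the printed coefficients, simulated power is 80.96 / 91.80 / 87.89 / 88.73 / 87.44% (linear, sigmoid Emax 1, sigmoid Emax 2, Emax, quadratic). Table 10-2 gives 80.84 / 91.81 / 87.80 / 88.72 / 86.61%. The small quadratic gap fits coefficient rounding: scaled to a peak of exactly 40 m, that shape gives 86.9%.

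**2. Height of each planning curve on (0, 40] mg.**
- Linear: 40.0 m at 40 mg.
- Sigmoid Emax 1: 40.1 x 40^4/(9^4 + 40^4) = 39.997 m.
- Sigmoid Emax 2: 45 x 64000/72000 = 40.0 m.
- Emax: 41.25 x 40/41.25 = 40.0 m.
- Quadratic: 2.667^2/(4 x 0.044) = 40.41 m, at 30.3 mg.

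Delta = 40 m therefore sits at the top of every curve.

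**3. Hand check, linear shape.** SE of the fitted maximum = 80 x 40/sqrt(sum n_i(d_i - mean)^2). The sum is 108450 - 3690^2/216 = 45412.5, with square root 213.1, so SE = 15.02 m. If the true maximum is 40 m, the fitted maximum falls below 40 m half the time. Significance on this contrast alone, at the simulated critical value of 1.966, needs a fitted maximum above 1.966 x 15.02 = 29.5 m. The chance of that is Phi((40 - 29.5)/15.02) = Phi(0.697) = 0.757. The share of those below 40 m is (0.757 - 0.500)/0.757 = 34%. This treats the SD as known and ignores the other four contrasts.

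**4. Full simulation.** 30,000 trials per shape, each shape scaled to a true maximum of 40 m, with model parameters refitted by least squares (ED50 0.04-60 mg, Hill 0.5-10). The SAP text states no selection rule, so three were tried. The table shows the share of signalled trials whose fitted curve stays below 40 m.

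| True shape | Largest contrast | Lowest AIC | Any significant model |
|---|---|---|---|
| Linear | 40.8% | 34.6% | 30.9% |
| Sigmoid Emax 1 | 31.5% | 24.3% | 22.5% |
| Sigmoid Emax 2 | 34.2% | 27.9% | 25.3% |
| Emax | 36.1% | 31.7% | 29.0% |
| Quadratic | 37.3% | 30.2% | 28.0% |

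Narrower bounds (ED50 1-60 mg, Hill 1-6) give 30.0-40.1%, 23.6-35.0% and 22.2-31.6% for the three rules. Holding shape parameters at their planning values and taking the largest contrast, 40 m is reached in 58.7-67.8% of signalled trials, so it is missed in 32.2-41.3%.

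**5. What the misses look like.** In trials that miss 40 m, the median fitted maximum is 34.2-35.2 m, and it is at least 35 m in 43-52% of them, although the true maximum is 40 m throughout. At an illustrative Delta of 30 m (not from the documents), the MED is absent in 3.2-7.9% of signalled trials across the three rules.

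**The case against.** The strongest reply is that 40 m is stated as the clinically relevant change. If the fitted curve does not reach it, the MED definition has worked: no dose in the range attains the relevant effect. Powering a trial at its relevant effect is common, and an estimate of a quantity equal to the threshold must fall below it about half the time before conditioning on significance. The further Deltas are optional and feed no test. A reader can take the dose for any Delta off the plotted curve. Dose choice also draws on other efficacy variables and safety, and Protocol section 4 says the totality of the data will be weighed.

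Most of this stands. A reader might infer that an unreached 40 m is lost information, or that setting Delta equal to the planned maximum is itself an error. The documents support neither. The absence of a stated model-selection rule, or of a sentence on reporting an unreached MED, might also look like part of the defect. These are missing details: the cited method sources may hold a selection rule, and not reached follows from the definition.

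The reply does not remove the conflict between the two documents. A clinical threshold should not come from the trial's own results. A charitable reading is that the values would be fixed at the blind review (SAP 4.6), but the Step 2 sentence does not say so.

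**Conclusion.** The point holds as a protocol-SAP conflict with a practical consequence. The protocol requires any further Deltas to be in the SAP; the SAP contains none and allows them to be set from the results. Because the only fixed Delta equals the assumed maximum effect, the situation in which a further Delta would be wanted is common: roughly 22-41% of signalled trials under the plan's sample size, SD and shapes. The selection rules and fitting bounds are assumptions of this check. If the true maximum is smaller, 40 m is reached less often still: with the correct shape fixed and no conditioning on significance, the chance of a fitted maximum of at least 40 m is 21-25% at a true maximum of 30 m, and 6-9% at 20 m.

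A reader might go further and conclude that the proof-of-concept test is compromised or that the trial cannot inform dose choice. Neither follows. Step 1 power and type I error do not involve Delta, and the curve with its bands and the pairwise intervals remain. What is at stake is whether an MED at any value other than 40 m can be presented as planned. The change should be made.

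**What to change.** In SAP 6.2.1.2, Step 2:

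- Remove the words that tie the further Deltas to the observed data.
- Keep 40 m.
- List the further Delta values before unblinding, including at least one below 40 m that the sponsor agrees is clinically relevant. The documents give no such value, so none is proposed here.
- State that any Delta added later will be labelled post hoc and exploratory.

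A dose reaching a fixed fraction of the fitted maximum may be added as a descriptive output, but it does not replace a Delta. It exists however small the maximum is, and for a linear fit the fraction p always returns p x 40 mg, whatever the positive slope.

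The cost is a wording change and a few extra estimates from the same fitted model. The downside is that the values must be agreed before unblinding.
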